6.12.6. Vital Signs and Other Physical Findings

Vital signs will be listed by patient, cycle and cycle day (baseline, Day 1 of each cycle, Day 14 of Cycles 1 and 2 only, and Visit 801). This listing will include height (at baseline), weight, heart rate, blood pressure, and ECOG performance status.

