### **5.1.3. Clinical Pharmacokinetics of LY2157299**

As of 07 September 2012, based on 5 dose-escalation cohorts (40-, 80-, 160-, 240-, and 300-mg doses), a total of 717 plasma concentration observations from 37 patients from Study H9H-MC-JBAH (JBAH) were obtained. LY2157299 was rapidly absorbed with plasma concentrations measurable for at least 48 hours. No accumulation upon multiple dosing of LY2157299 in the 5 cohorts was observed over the 14-day BID dosing regimen. The median  $t_{1/2}$  ranged between 6 to 8 hours across dose levels. On Day 14, the median time to maximum concentration at steady state ranged from 0.5 to 2 hours postdose, independent of dose. Both the maximum observed concentration at steady state and exposure approximately doubled with a 2-fold increase in dose. The population PK of LY2157299 was best described by a 2-compartment model with first-order absorption and elimination. LY2157299 was rapidly absorbed into the systemic circulation with an absorption rate constant of 2.2/h. The mean population apparent clearance (CL/F) of LY2157299 was 38 L/h, and the steady state volume of distribution was 193 L. The between-patient variance for plasma total CL/F and exposure was moderate (46%), and between-occasion variance was low (18%). Systemic exposure to LY2157299 was not influenced by age, smoking status, alcohol consumption, body mass index, or ethnicity in this model developed mainly from glioblastoma (GBM) patient data.

Preliminary simulations of the median exposures (20th-80th percentile) following administration of 160 mg and 300 mg in patients with HCC (Study H9H-MC-JBAK [JBAK]) (n=137) were 3.8 (1.7-7.3) and 7.0 (3.5-13.6) mg\*h/L, respectively (Raymond et al. 2013). Between-patient variability on apparent CL/F was moderate (at 42%) in HCC patients. Preliminary PK data suggest that some patients at the 300-mg dose might reach higher exposures than previously observed for the same dose level in patients with GBM. LY2157299 will be fully eliminated after a 14-days-off period.

For additional information, see Section 6.1 in the IB.

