### **5.1.4. Nonclinical Toxicology of LY2157299**

The toxicity of LY2157299 has been characterized in repeat- and intermittent-dose, nonclinical safety studies up to 6 months duration in the rat and dog. The following paragraphs summarize the major findings in rats and dogs.

The heart and great vessels are major target organs for toxicity in both F344 rats and beagle dogs following treatment with LY2157299. These effects include valvulopathy and vascular lesions of multiple blood vessels at the base of the heart in rat and dog, which in the rat appear to be

partially reversible. In the rat, a continuum of changes in the gastrointestinal (GI) tract have been described, including inflammation of the mucosa, simple mucosal hyperplasia, and adenocarcinoma following 6 months of continuous treatment. Based on safety pharmacology studies, administration of LY2157299 produced increases in hexobarbital-induced sleep time. Administration of LY2157299 may produce dose-dependent hemodynamic side effects, measured by decreased blood pressure and increases in heart rate, which can be easily monitored in the clinic and are reversible upon cessation of treatment. The nonclinical data do not reveal any substantive clinical risk of QT/corrected QT prolongation at doses that result in total plasma concentrations of at least 3.3 µg/mL.

LY2157299 was negative in a bacterial mutation test (Ames test) and an in vivo mammalian test (mouse micronucleus). However, LY2157299 was positive in an in vitro mammalian test (chromosome aberration) with and without S9 activation. This positive finding is considered acceptable in the intended patient population.

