## **Attachment 1. Protocol JBAS Study Schedule**

---

Study Schedule, Protocol H9H-MC-JBAS – Study Period

Cycle (Visit)	Baseline (Visit 0)			Patient on Study Treatment									Post Discontinuation Follow-Up Periods		Comments	
				Cycle 1 (Visit 1)			Cycle 2 (Visit 2)			Cycle 3, n a (Visit 3, etc)			30-Day Safety Follow-Up (v801)	Long-Term Follow-Up b (v802, v803, etc)		
Relative Day Within a Cycle	≤28	≤14	≤7	1c,d	8c	14c	15	22	1c	14c,e	22	1c			14c,e	
Procedures																
Informed consent	X															Informed consent must be signed prior to performing any study procedures.
Medical history		X														
Child-Pugh, BCLC, and CLIP staging			X f													
Physical exam including vital signs (heart rate, blood pressure, weight)		X		X		X			X	X		X		X		Starting in Cycle 3, to be performed once per cycle
CTCAE grading		X		X		X			X	X		X		X	X g	Starting in Cycle 3, to be performed once per cycle
Concomitant medications		X		X					X			X	X	X	X	During long-term follow-up collect only therapy provided to patient for HCC
ECOG performance status		X		X		X			X	X		X		X		Starting in Cycle 3, to be performed once per cycle
Survival data														X		Every 60 days ±7 days

Cycle (Visit)	Baseline (Visit 0)			Patient on Study Treatment									Post Discontinuation Follow-Up Periods		Comments	
				Cycle 1 (Visit 1)			Cycle 2 (Visit 2)			Cycle 3, na (Visit 3, etc)			30-Day Safety Follow-Up (v801)	Long-Term Follow-Up b (v802, v803, etc)		
Relative Day Within a Cycle	≤28	≤14	≤7	1 c,d	8 c	14 c	15	22	1 c	14 c,e	22	1 c			14 c,e	
Tumor assessment, physical (palpable or visible)		X		X					X			X		X		
Imaging procedures																
Echocardiography with Doppler h	X								X			X		X i	X i	Cycle 2, 3, 4, and every other cycle (Cycle 6, Cycle 8, etc)
Chest CT scan or Chest MRI		X												X j		CT scan or MRI every 6 months (for cardiac assessment)
Tumor assessment, radiological		X								X			X	X k	X k	Chest CT scan with contrast of thorax and abdomen ( with both arterial and portal phase imaging of the liver for mRECIST) or MRI for tumor assessment every 6 weeks (± 3 days) starting Cycle 2 Day 14
ECG		X							X			X		X i	X i	Cycle 2, 3, 4, and every other cycle (Cycle 6, Cycle 8, etc)

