Abbreviations: AFP = alpha-fetoprotein; aPTT = activated partial prothrombin time; BCLC = Barcelona Clinic Liver Cancer; BNP = brain natriuretic peptide; BSC = best supportive care; C = cycle; CLIP = Cancer of the Liver Italian Program; CT = computed tomography; CTCAE = Common Terminology Criteria for Adverse Events; DCE-MRI = dynamic contrast-enhanced magnetic resonance imaging; DW-MRI = diffusion-weighted magnetic resonance imaging; ECG = electrocardiogram; ECOG = Eastern Cooperative Oncology Group; eGFR = estimated glomerular filtration rate; EORTC = European Organisation for Research and Treatment of Cancer; exam = examination; GBCA = gadolinium-based contrast agent; HBsAg = hepatitis B surface antigen; HCC = hepatocellular carcinoma; INR = international normalized ratio; MAP = multi-analyte panel; mRECIST = modified Response Evaluation Criteria in Solid Tumors; MRI = magnetic resonance imaging; PF4 = platelet factor 4; PGx = pharmacogenomics; PIVKA II = prothrombin induced by vitamin K absence; PK = pharmacokinetic; PT = prothrombin time; QLQ = quality-of-life questionnaire; RNA = ribonucleic acid; TGF- $\beta$  = transforming growth factor beta.

- a Patients on study for more than 1 year (before entering extension period) only need tests to be performed on Day 1 of each cycle.
- b Follow-up consists of Visit 802 and all subsequent visits (60 days  $\pm$  7 days).
- c To be performed predose LY2157299 or sorafenib
- d A delay at the start of a cycle (Day 1) of no more than 3 days because of holidays, weekends, inclement weather, or other justifiable events will be permitted and not counted as a protocol violation.
- e In extenuating circumstances, the “on study drug” window for LY2157299 is allowable from Day 10 to Day 14.
- f Child-Pugh, BCLC, and CLIP assessment procedures can be found in [Attachment 6](#), [Attachment 7](#), and [Attachment 8](#), respectively.
- g If drug-related toxicity is present 30 days after the last cycle of study drug, patients must be followed up approximately every 30 days until toxicity resolution, stabilization, another therapy is initiated, or death.
- h Echocardiography with Doppler can be performed up to 3 days prior to Day 1.

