- i If the patient has clinically significant cardiac findings at discontinuation (Visit 801), echocardiography with Doppler and ECG and ECG chemistry will be repeated every 2 months for 6 months (Visits 803, 804, and V805). If there are no cardiac findings at discontinuation (Visit 801), 1 more echocardiography with Doppler, ECG, and ECG chemistry will be performed after 2 months (Visit 802) unless a patient is receiving another treatment (see Section [10.3.2.2](#)).
- j If there were no clinically significant findings at the last assessment conducted within the 30 days following discontinuation and the patient has started another treatment, Visit 801 CT scan or chest MRI with contrast will not be performed.
- k Repeat radiological scans at study discontinuation may be omitted if a patient has objective disease progression or if imaging has been performed in the previous 3 to 6 weeks.
- l Within 60 days prior to randomization; includes HBsAg, hepatitis B surface antibody, total hepatitis B core antibody, hepatitis B e antigen, hepatitis B e antibody, hepatitis B virus DNA, hepatitis C RNA.
- m HBsAg carriers should be closely monitored with assessment of hepatitis B serology during the study treatment and 30-day safety follow-up period.
- n  $\pm$ 3 days after end of treatment with LY2157299.

Study Schedule, Protocol H9H-MC-JBAS: Extension Period

Cycle (Visit)	Study Treatment (v501, v502, etc) a	Post Discontinuation Follow-Up Periods		Comments
		30-day Safety Follow-Up (v801)	Long-Term Follow-Up b (v802)	
Refer to Section 10 of the protocol for descriptions of the study periods				
Procedures				
Physical exam	X	X		Performed once per cycle on Day 1 of each cycle in extension period
Vital signs (heart rate, blood pressure, weight)	X	X		Performed once per cycle predose on Day 1 of each cycle in extension period
CTCAE grading	X	X	X c	Performed once per cycle predose on Day 1 of each cycle in extension period
Concomitant medications	X	X	X	Performed once per cycle predose on Day 1 of each cycle in extension period
Performance status	X	X		Performed once per cycle predose on Day 1 of each cycle in extension period
Imaging procedures				
Echocardiography with Doppler d	X	X e	X e	For patients receiving galunisertib: Performed once per cycle predose on Day 1 of every other cycle in the extension period.

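### From Cycle 3 no scheduled blood pressure or heart rate reading is taken while the patient is on LY2157299, although the protocol describes a reversible effect on both as easy to monitor in the clinic

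*SAP*

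**What the plan says.** Protocol 5.1.4, on nonclinical toxicology, states: "Administration of LY2157299 may produce dose-dependent hemodynamic side effects". It describes these as "measured by decreased blood pressure and increases in heart rate, which can be easily monitored in the clinic and are reversible upon cessation of treatment". Protocol 5.1.3 adds: "LY2157299 will be fully eliminated after a 14-days-off period".

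The measurement schedule is as follows.

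- **SAP 6.12.6** lists vital signs at baseline and on "Day 1 of each cycle, Day 14 of Cycles 1 and 2 only, and Visit 801". The output is a listing by patient, cycle and cycle day. No summary or change from baseline is planned.
- **Protocol Attachment 1, study period**, agrees. Vital signs are marked on Days 1 and 14 of Cycles 1 and 2. From Cycle 3 only the Day 1 cell is marked, with the comment "Starting in Cycle 3, to be performed once per cycle". Footnote c, attached to the Day 1 and Day 14 columns, reads "To be performed predose LY2157299 or sorafenib".
- **Protocol Attachment 1, extension period**, has vital signs "Performed once per cycle predose on Day 1 of each cycle in extension period".

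**The concern.** An effect that reverses when the drug stops can be seen only while the drug is present. From Cycle 3 the scheduled readings all fall at the end of the LY2157299-free part of the cycle, when such an effect would be expected to have gone. The schedule therefore does not deliver the monitoring that Protocol 5.1.4 relies on.

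Arm 1 (LY2157299 monotherapy) matters most. Protocol 8.2 says that arm is there to compare the safety of LY2157299 with that of sorafenib. Sorafenib is taken every day, so a Day 1 reading in Arms 2 and 3 is made during sorafenib treatment, whereas a Day 1 reading after Cycle 1 is never made during LY2157299 treatment. Anyone reading the vital-sign listing for later cycles is looking at off-LY2157299 values, and the SAP does not say so.

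**Working it through.** The documents state no figure to reproduce. The check sets the schedule against the pharmacokinetics.

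**Inputs**

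- Half-life 6 to 8 h, time to peak 0.5 to 2 h, absorption rate constant 2.2/h, no accumulation (Protocol 5.1.3).
- Doses 10 to 12 h apart (Protocol 9.4).
- Cycle length 26 to 31 days; LY2157299 dosing period 10 to 14 days (Protocol 8.1).

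**1. Is a Day 1 reading off LY2157299?**

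Off-drug interval = cycle length minus dosing period.

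- Shortest: 26 − 14 = 12 days.
- Nominal: 28 − 14 = 14 days.
- Longest: 31 − 10 = 21 days.

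Fraction remaining = 2^(−hours off / half-life).

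| Days off | Hours | Half-lives (8 h / 6 h) | Fraction left at 8 h |
|---|---|---|---|
| 12 | 288 | 36 / 48 | 1.5 × 10⁻¹¹ |
| 14 | 336 | 42 / 56 | 2.3 × 10⁻¹³ |
| 21 | 504 | 63 / 84 | 1.1 × 10⁻¹⁹ |

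Sensitivity: Protocol 5.1.5.1 gives lower clearance in HCC than in glioblastoma (25.4 against 38.4 L/h). If the volume is unchanged, the half-life rises by 38.4/25.4 = 1.51, to 9.1 to 12.1 h. Twelve days off is then still 288/12.1 = 23.8 half-lives. Every Day 1 reading from Cycle 2 on is off LY2157299.

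**2. How much drug is present at the Day 14 predose reading?**

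One-compartment oral model at steady state, with ke = ln 2 / half-life and interval τ:

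C(t) ∝ e^(−ke·t)/(1 − e^(−ke·τ)) − e^(−ka·t)/(1 − e^(−ka·τ)), and trough/peak = C(τ)/max C(t).

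| Half-life | τ = 10 h | τ = 12 h |
|---|---|---|
| 6 h | 0.38 | 0.31 |
| 8 h | 0.49 | 0.41 |

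The modelled peak is at about 1.2 to 1.3 h, inside the stated range. The protocol's own model has two compartments, but its rate constants are not given. If 6 to 8 h is the terminal half-life, an earlier distribution phase would lower these fractions. The HCC half-lives from step 1 would raise them, to 0.46 to 0.62. Roughly 30% to 50% is a working figure, not a precise one.

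**3. Count of scheduled readings on LY2157299, per patient**

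| | On drug, trough | On drug, near peak |
|---|---|---|
| Cycles 1-2 | 2 | 0 |
| Each cycle from Cycle 3, and the extension | 0 | 0 |

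The two are a maximum. The dosing period may end as early as Day 10, so a Day 14 reading is not always on drug.

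**4. Do other measurements fill the gap?**

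- On-treatment ECGs are on Day 1. Echocardiograms, at which Attachment 14 has blood pressure recorded, are on Day 1 or up to 3 days before. The shortest case is 12 − 3 = 9 days off, or 216/8 = 27 half-lives. These too are off LY2157299.
- Protocol 9.4.1.2 asks for regular blood pressure checks in patients on sorafenib, at unspecified times. Arm 1 has no equivalent.
- Day 14 attendance exists from Cycle 3: hematology, serum chemistry and special chemistry are marked there. On Cycle 1 Day 14, Attachment 5 has a PK sample at 0.5-2 hours. Vital signs are attached to neither.

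**The case against.** Fewer repeat readings after two cycles is a defensible saving of effort. With no accumulation and full washout, each cycle repeats a similar exposure, so the two early Day 14 readings bear on later cycles. Adverse events are evaluated at every visit and reported between visits, and clinically significant vital-sign findings that lead to a diagnosis are reportable. The main nonclinical worry, valvular and vascular lesions, is followed by echocardiography, ECG, cardiac markers and chest imaging, and SAP 6.12.7 does not count vital signs among the cardiac assessments. All of this stands, and it limits the point to scheduled vital signs.

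It does not remove the point. Two trough readings cannot show an effect at peak or an on-drug effect in later cycles, and event reporting will not pick up an asymptomatic shift.

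Four stronger readings are tempting, and the documents do not support them.

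- *That the protocol expects the effect.* Section 5.1.4 speaks of a possibility, from nonclinical data, and Protocol 5.1.5 reports no cardiovascular toxicity in 218 patients.
- *That the effect escapes ascertainment altogether.* The early readings and adverse event reporting remain.
- *That a planned arm comparison is distorted.* SAP 6.12.6 plans only a listing, and that listing already carries cycle day.
- *That a given share of treatment time lies beyond Cycle 2.* The documents give no time on treatment. Time to progression is a poor stand-in, because patients may continue past progression or stop for toxicity.

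**Conclusion.** The point holds as an inconsistency between Protocol 5.1.4 and the measurement schedule. At most two scheduled vital-sign readings per patient are made on LY2157299, both at trough. None is made near peak, and none from Cycle 3 onward. The absence of drug on Day 1 does not depend on the model: it follows from Protocol 5.1.3 and survives every half-life tried. The 30% to 50% trough figure does depend on the one-compartment approximation and on pharmacokinetics drawn mainly from glioblastoma patients.

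The consequence is modest. No planned analysis is biased and safety follow-up continues. What is missing is quantitative on-drug blood pressure and heart rate data, above all in Arm 1, where LY2157299 is given alone. It is worth correcting because the visits needed already exist.

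**What to change.** Reconcile Protocol 5.1.4 with Attachment 1 and SAP 6.12.6.

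1. **Add, rather than move, a reading.** From Cycle 3, take blood pressure and heart rate at the existing Day 14 visit as well as on Day 1, for as long as that visit is scheduled. Footnote a of Attachment 1 limits patients beyond 1 year to Day 1 tests. Record the time since the last LY2157299 or placebo dose, since Day 14 remains a predose reading and dosing may have ended earlier.
2. **Take one reading near peak.** On Cycle 1 Day 14, measure blood pressure and heart rate at the 0.5-2 hour PK sample.
3. **Summarise as well as list.** In SAP 6.12.6, give change from baseline by arm, separately for on-drug (Day 14) and off-drug (Day 1) readings.
4. **Label the rest.** State that vital signs after year 1 and in the extension period are Day 1 only and are off LY2157299.

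The cost is one extra cuff reading per cycle, a small table and a site-training note, with no new visit. If data collection is too far advanced for items 1 and 2, items 3 and 4 can still be done with the readings already planned, with the limitation stated in the study report.

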6.12.7. Cardiac Assessments

Cardiac assessments include ECG, echocardiography, chest computed tomography (CT) scan and/or MRI, ECG chemistry (see Section [6.12.3 Clinical Laboratory Evaluation](#)) and cardiac related adverse events (SOC=“cardiac disorders”; see Section [6.12.2 Adverse Events](#)).

If the patient has clinically significant cardiac findings at discontinuation (Visit 801), echocardiography, ECG and ECG chemistry will be repeated every 2 months for 6 months (Visits 803, 804, and 805).

If there are no clinically significant cardiac findings at discontinuation (Visit 801), 1 more echocardiography, ECG, and ECG chemistry will be performed after 2 months (Visit 802). If a patient receives another treatment, Visit 802 cardiac assessments will not be performed.

The monitoring described in the above 2 paragraphs also applies to patients in the extension period. Therefore, for these cases, the patient does not discontinue from the study at the end of the 30-day safety follow-up period but after the cardiac findings have either resolved or, if not resolved after 6 months, after discussions between the Lilly CRP and investigator.

A central reading will be performed for ECG, and CT and MRI images and will be used in the study report.

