**5.1.4.1. Overall Conclusions**

Collectively, the findings in the continuous 3- and 6-month daily-dosing toxicity studies, particularly the degeneration of the large blood vessels, imply that long-term, daily dosing of LY2157299 may carry a risk in patients for developing aneurysms. Reversibility was not assessed in the 3- or 6-month toxicity studies, but in a non-GLP reversibility study in rat, data indicate the cardiovascular lesions are partially reversible; but those lesions that are still present following the recovery period are still adverse. The intermittent-dosing regimen in patients is based on the safety demonstrated in the rat and dog following 1 month of continuous daily dosing in which the NOELs for any effects in the heart were 150 and 20 mg/kg in the rat and dog, respectively, and a 3-month intermittent-dosing study in the rat in which the NOEL for any effects in the heart was 50 mg/kg (see [Table JBAS.5.2](#) for margin-of-safety calculations). Although the likelihood of occurrence or the extent and timing of such a risk observed after daily dosing is not known in humans, LY2157299 will be administered as an intermittent-dosing regimen in this patient population that has a poor prognosis and rapidly advancing cancer.

concerns arise during regular safety reviews. At this time, no clear or definitive drug-related toxicity profile has emerged.

The most common treatment-emergent adverse events (TEAEs) related to LY2157299 monotherapy were fatigue, nausea, and vomiting. All other events occurred in <5% of the patient population. Most TEAEs were of mild or moderate severity.

A total of 155 serious adverse events (SAEs) have been reported in the clinical and safety databases. Forty-five SAEs considered to be related to LY2157299 have been reported among 26 patients. Of these, 18 patients receiving LY2157299 monotherapy reported a total of 31 treatment-related SAEs, and 8 patients receiving LY2157299 combination therapies reported a total of 14 treatment-related SAEs. For the monotherapy, the most common treatment-related SAEs (occurring in 2 or more patients) included anemia, thrombocytopenia, neutropenia, GI hemorrhage, and diarrhea. None of the treatment-related SAEs occurring with the combination therapies occurred in 2 or more patients.

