A total of 15 deaths due to causes other than study disease have been reported. Infection-related deaths were observed in 4 cases, and GI-related deaths were reported in 3 cases. Additionally, not-yet-determined or unknown causes of death were reported in 6 cases; 2 deaths, occurring with monotherapy, were reported by investigators to be potentially associated with study drug. However, in reviewing the specific cases, the rationale for causality with LY2157299 appears to be uncertain.

Study H9H-MC-JBAN, to evaluate the safety of LY2157299 in Japanese patients, has been initiated. The first cohort (150 mg/day, 3 patients) completed Cycle 1 without significant toxicity. The second cohort (300 mg/day) is currently ongoing with the first 2 patients having completed Cycle 1 without significant toxicity.

Due to the preclinical cardiovascular toxicity findings, comprehensive cardiovascular monitoring has been conducted for all patients receiving LY2157299 (echocardiography/Doppler, cardiac markers [brain natriuretic peptide {BNP}, troponin I], electrocardiogram [ECG], chest magnetic resonance imaging [MRI] or computed tomography [CT] with contrast). To date, no cardiovascular toxicity has been observed in the 218 patients enrolled in the LY2157299 clinical trials.

In summary, LY2157299 shows a toxicity profile that justifies its use as monotherapy and in combination with radiochemotherapy and with chemotherapy.

For additional information, see the IB.

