**ECG chemistryb**

Lipase  
 Thyroid stimulating hormone  
 Tri-iodothyronine  
 Thyroxine  
 Calciumc  
 Glucose, random (nonfasting)c  
 Albuminc  
 Phosphorusc  
 Sodiumc  
 Potassiumc  
 Magnesiumc

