6.12.3. Clinical Laboratory Evaluation

Table [JBAS.6.6](#) describes the clinical laboratory tests to be performed and whether the test will be performed locally or centrally:

Table JBAS.6.6. Clinical Laboratory Tests

Hematology^a	Clinical chemistry^b
Hemoglobin	Serum concentrations of:
Erythrocyte count (RBC)	Total bilirubin
Leukocytes (WBC)	Direct bilirubin
Neutrophils, segmented + bands	Total protein
Lymphocytes	Alkaline phosphatase
Monocytes	LDH
Eosinophils	Creatine kinase
Basophils	Alanine aminotransaminase/serum glutamic pyruvic transaminase
Platelets	Aspartate aminotransferase/ Serum glutamic oxaloacetic transaminase
	Blood urea nitrogen
Immunophenotype^b	Creatinine
Urinalysis^a	Uric acid
Specific gravity	Calcium
pH	Glucose, random (nonfasting)
Protein	Albumin
Glucose	Cholesterol
Ketones	Phosphorus
Blood	Sodium
Leukocyte esterase	Potassium
	Magnesium
ECG chemistry^b	Serum markers^b
Lipase	AFP
Thyroid stimulating hormone	AFP L3
Tri-iodothyronine	PIVKA II
Thyroxine	E-cadherin
Calcium ^c	
Glucose, random (nonfasting) ^c	TGF-β+PF4^b
Albumin ^c	Coagulation^b
Phosphorus ^c	aPPT
Sodium ^c	PT
Potassium ^c	INR
Magnesium ^c	
Special chemistry^b	Fibrotest^b
Cystatin C	Urine C-terminal telopeptides of Type 1 Collagen^b
Troponin I	
BNP	MAP^b
High-sensitivity C-reactive protein	Serum pregnancy test (females only)^a
Hepatitis B and C serology and panels^b	
Hepatitis B surface antigen	
Hepatitis B surface antibody	
Total hepatitis B core antibody	
Hepatitis B e antigen	
Hepatitis B e antibody	
Hepatitis B virus DNA	
Hepatitis C RNA	

Clinical Laboratory Tests (Abbreviations)

Abbreviations: AFP = alpha-fetoprotein; aPTT = activated partial prothrombin time; BNP = brain natriuretic peptide; ECG = electrocardiogram; INR = international normalized ratio; LDH = lactate dehydrogenase; MAP = multi-analyte panel; PF4 = platelet factor 4; PIVKA II = prothrombin induced by vitamin K absence; PT = prothrombin time; RBC = red blood cell; TGF- β = transforming growth factor beta; WBC = white blood cell.

- a Performed at local laboratory.
- b Performed at central laboratory. Performed at a local laboratory if performed during the treatment extension period.
- c Test not performed if both chemistry and ECG chemistry are required.

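### SAP 6.12.7 defines the cardiac assessments incompletely: troponin I and BNP have no named by-arm summary, and cardiac adverse events are limited to one organ class

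*SAP*

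**What the plan says.** SAP 6.12.7 defines the cardiac assessments in one sentence: "Cardiac assessments include ECG, echocardiography, chest computed tomography (CT) scan and/or MRI, ECG chemistry" (with a pointer to 6.12.3), "and cardiac related adverse events (SOC=“cardiac disorders" (with a pointer to 6.12.2). Its subsections cover ECG, echocardiography and chest CT. Neither the sentence nor the subsections mention special chemistry.

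The panels are set out in protocol Attachment 2 and SAP Table JBAS.6.6. ECG chemistry holds lipase, thyroid tests (for example "Thyroid stimulating hormone"), glucose, albumin and electrolytes. Special chemistry holds cystatin C, troponin I, BNP and high-sensitivity C-reactive protein.

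The protocol's summary of clinical experience, just ahead of Section 5.1.5.1, describes the programme's cardiovascular monitoring as including "cardiac markers [brain natriuretic peptide {BNP}, troponin I". Section 5.1.5.1 counts troponin I and BNP among the cardiac toxicity monitoring of the earlier HCC study. On toxicology, Section 5.1.4 states: "The heart and great vessels are major target organs for toxicity in both F344 rats and beagle dogs". Section 5.1.4.1 adds that long-term daily dosing "may carry a risk in patients for developing aneurysms". This trial doses intermittently for that reason.

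**The concern.** Protocol Section 8.2 justifies the monotherapy arm partly by a safety comparison with sorafenib. It stresses this because LY2157299 has shown preclinical cardiac toxicity and sorafenib has known cardiac toxicity in patients. Section 12.2.11 commits the safety analyses to observations that target cardiac monitoring. A reader would expect the cardiac section of the SAP to carry the two named cardiac markers, and to gather adverse events of the heart and great vessels in one place by arm. As written, it does neither explicitly. A by-patient listing is a poor basis for comparing arms of 30, 60 and 30 patients. A small number of related events spread over several organ classes is also easy to miss in general tables.

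**Working it through.** The plan states no figure on this point, so the check is a side-by-side reading.

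**1. Does the named panel contain the cardiac markers?** (Attachment 2; SAP Table JBAS.6.6)

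- ECG chemistry has 11 analytes: lipase, TSH, tri-iodothyronine, thyroxine, calcium, glucose, albumin, phosphorus, sodium, potassium and magnesium. Troponin I or BNP among them: 0 of 11.
- Seven of these carry footnote c: "Test not performed if both chemistry and ECG chemistry are required". When both panels are due, 11 − 7 = 4 remain: lipase and the three thyroid tests.
- Special chemistry has 4 analytes. Troponin I and BNP are 2 of the 4.

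**2. Does the protocol treat special chemistry as cardiac monitoring?** In the extension-period schedule (Attachment 1), echocardiography, ECG, ECG chemistry, cardiac CT/MRI and special chemistry are all tied to patients receiving galunisertib. Hematology and serum chemistry carry no such restriction. Special chemistry is thus handled with the cardiac set, and SAP 6.12.7 leaves it out.

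**3. What output does each item get in the SAP?**

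| Item | Specified output | Summary named? |
|---|---|---|
| ECG parameters (6.12.7.1) | Listing; change from baseline at each visit | Yes |
| Valve regurgitation (6.12.7.2) | Listing; maximum shift by treatment | Yes |
| Ejection fraction and other echo measurements (6.12.7.2) | Listing of values and changes; LVEF graph if needed | No |
| Chest CT/MRI for cardiac assessment (6.12.7.3) | Listing | No |
| Troponin I, BNP (6.12.3, as special chemistry) | Listing with reference ranges and out-of-range flags | No |
| Adverse events, all organ classes (6.12.2) | Counts and percentages by treatment, organ class and preferred term | Yes, but no cardiovascular grouping |

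Section 6.12.2 also plans a table of shifts in laboratory CTCAE grade. Section 6.12.3 limits grading to relevant hematology and chemistry and does not say whether troponin I or BNP counts as relevant. They may appear there, but the plan does not commit to it.

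**4. What does the one-class definition exclude?** Any event coded outside cardiac disorders. The documents do not say where terms for aneurysm, raised troponin, reduced ejection fraction or QT prolongation are coded. That some fall in another class is an assumption. The definition makes no provision for them if they do.

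**5. Scale of a single event.** With the planned arm sizes, one patient is 1/30 = 3.3 percentage points in the monotherapy or control arm, and 1/60 = 1.7 points in the combination arm. This shows only that counts will be small enough for grouping to affect what is seen. It does not estimate how many events are affected.

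**The case against.** The strongest reply is that the sentence in 6.12.7 drives no output of its own. It says the assessments include certain items, which need not be exhaustive, and it refers to 6.12.2 and 6.12.3 for laboratory data and adverse events. In 6.12.3, serum, special and ECG chemistry are treated alike, so troponin I and BNP already get the reporting that ECG chemistry gets. No composite cardiac table exists from which anything is filtered out. All of this stands. It means that merely adding a panel name would change nothing, and the fix has to specify tables.

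Three stronger readings are tempting and are not supported:

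- *That ECG chemistry is the wrong panel.* Protocol Section 10.3.2.2 itself pairs ECG chemistry with echocardiography and ECG in cardiac follow-up after discontinuation. The SAP follows the protocol here. The fault is omission.
- *That great-vessel findings fall outside the cardiac analysis.* Protocol Section 10.3.2.2 gives evaluation of the large vessels as the purpose of the cardiac chest CT. That CT (or MRI) is in the 6.12.7 definition, is read centrally, and is listed in 6.12.7.3. Only the grouping of adverse events is affected.
- *That events, perhaps several per arm, would be lost.* Every treatment-emergent event is tabulated by arm, organ class and preferred term, and serious events and deaths have their own tables. The protocol reports no cardiovascular toxicity in 218 patients treated so far, so nothing in the documents supports a count of several per arm.

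What the reply does not meet is that no by-arm summary of the two cardiac markers is promised, and no grouping brings heart and great-vessel adverse events together.

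**Conclusion.** The point holds as a gap in definition and summary. From the documents alone, 6.12.7 omits special chemistry, and troponin I and BNP are certain only of a by-patient listing. It is also plain that cardiac adverse events are confined to one organ class while the nonclinical concern covers heart and great vessels. That some relevant events would code elsewhere is an assumption, since no mapping is given. If they all coded to cardiac disorders, the second part would have no practical effect. The consequence is a weaker between-arm view of cardiac safety, with no loss of data. No sample size, error rate or efficacy analysis is touched. The change is worth making because it is cheap and concerns the compound's main nonclinical safety signal.

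**What to change.** In SAP 6.12.7:

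1. Keep ECG chemistry and add special chemistry (troponin I, BNP) as a cardiac assessment. Specify by-arm summaries of change from baseline and a shift table for both markers.
2. Before database lock, replace the one-class definition with a prespecified list of cardiovascular terms covering heart, great-vessel and relevant investigation terms (troponin, BNP, ejection fraction, ECG/QT). Tabulate it by arm with a row for each term. A term list works whichever organ class the dictionary assigns.

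The cost is SAP wording, a short term list and a few more tables. The data are already scheduled: Attachment 1 has special chemistry at baseline, through treatment and at Visit 801. One downside needs handling. Hypertension is an expected sorafenib effect and could swamp the grouping, so it should have its own row or be kept out of the great-vessel terms.
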